10.6.3 Laboratory Test Results

Summary statistics over scheduled visits for actual values, changes from baseline of selected laboratory parameters below will be presented for subjects in the **Safety Analysis Set**.

1. **Corrected** Calcium
2. Magnesium
3. Total bilirubin
4. Direct bilirubin
5. Alkaline phosphatase
6. AST (SGOT)
7. ALT (SGPT)
8. Amylase
9. Lipase
10. Hemoglobin
11. Platelets
12. Neutrophils
13. Lymphocytes
14. LDH
15. Immunoglobulins (IgG, IgA, IgM)
16. Fibrinogen

Shift tables between the worst post-baseline and baseline grades for selected laboratory parameters will be provided.

The subject incidence of potential cases of Hy's Law will be summarized.

10.6.4 Vital Signs

The number and percentage of subjects with abnormal changes in systolic blood pressure, diastolic blood pressure and heart rate will **be** summarized based on **Safety Analysis Set**.

10.6.5 Physical Measurements

Not Applicable

10.6.6 Electrocardiogram (ECG)

Not Applicable

10.6.7 Antibody Formation

The incidence and percentage of subjects who develop anti blinatumomab antibodies (binding and if positive, neutralizing) and anti-pembrolizumab antibodies at any time will be tabulated.

10.6.8 Exposure to Investigational Product

Descriptive statistics will be produced to describe the exposure to blinatumomab and pembrolizumab. The number of cycles initiated, completed, discontinued, and re-started of blinatumomab and pembrolizumab will be summarized. **If a subject completed 85% of planned days on target dose, he/she is considered as completing a cycle.** In addition, the duration of therapy will be summarized by cycle and overall. **Relative dose intensity at the target dose will be calculated. It is the actual exposure duration at target dose divided by planned duration of target dose, which is 49 days for cohort Ia, and 42 days for cohort IIa and IIIa in cycle 1; and 21 days for cohort Ia, and 14 days for cohort IIa and IIIa in cycle 2. Subjects who didn't reach the target dose are considered having actual exposure duration as 0. Relative dose intensity at the target dose will be summarized by cycle.** The number and percent of subjects with dose modifications (eg, dose changes, dose interruptions) and reasons for modification will be summarized. **Analysis will be performed based on Safety Analysis Set.**

10.6.9 Exposure to Concomitant Medication

The number and percent of subjects receiving concomitant medications from study day 1 through blinatumomab or pembrolizumab safety follow-up, whichever is later will be summarized by preferred term as coded by the World Health Organization Drug (WHODRUG) dictionary. In addition, the number and proportion of subjects receiving

anti-cancer therapies during long term follow-up will be summarized **using Safety Analysis Set.**

10.6.10 Pharmacokinetic Analysis of Blinatumomab

Blinatumomab serum samples will be taken as listed in Schedule of Assessment of protocol. All data for PK analyses will be extracted from a secure folder and were mapped via the SAS_CDISC_v2 clinical connector into the Pharsight Knowledgebase Server (PKS) system version 4.0.3 (Pharsight®, St. Louis, MO).

Blinatumomab pharmacokinetic analysis will be performed using Phoenix WinNonlin v.6.4 software on Citrix (Pharsight®, St. Louis, MO) as part of the validated PKS system on individual serum blinatumomab concentrations to estimate the following PK parameters:

- The steady state serum concentration (C_{ss}) of cycle 1 summarized as the observed concentrations collected during continuous IV infusion by dose levels.
- Systemic clearance (CL) calculated as $CL=R_0/C_{ss}$; where R_0 is the infusion rate ($\mu\text{g/hr}$) and C_{ss} is the dose normalized average C_{ss} .

Nominal times were used for presenting data in tables. Blinatumomab concentrations below the lower limit of quantification (LLOQ, 50 pg/mL) were set to zero before data analysis. All individual PK parameters and descriptive statistics are presented to 3 significant figures, except for CV%, which was reported to 1 decimal place.

PK parameters such as steady state concentration (C_{ss}) will be estimated for patients who have evaluable PK data. Summary statistics, including mean, standard deviation, CV%, median, range (Minimal, Maximal), geometric mean and CV% of geometric mean will be computed for each pharmacokinetic parameter and grouped by dose, and treatment Phase. Individual concentration-time data will be tabulated and presented in PK appendix. Mean concentration-time profiles for each cohort may be provided, if sufficient data are available. **Analyses will be performed based on Pharmacokinetic Analysis Set.**

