7.3.14 Pharmacokinetic Assessments

7.3.14.1 Blinatumomab

Pharmacokinetic (PK) assessments will be required for all subjects receiving blinatumomab.

In cohort Ia, blinatumomab samples will be collected at day 1 (predose, 4, 6, 8 h after start of 9 µg/d infusion), day 2 (any time), day 8 (6 - 10 h after start of 28 µg/d infusion), day 10 (any time), day 15 (1 hour after pembrolizumab infusion has ended in cohort Ia), day 22 (any time), day 29 (any time) and day 43 (any time) in cycle 1. In cohorts IIa and IIIa, blinatumomab samples will be collected on day 1 (predose, 4, 6, 8 hours after start of 9 µg/d infusion), day 2 (any time), day 8 (6 -10 hours after start of 28 µg/d infusion), day 10 (any time), day 15 (prior to start of 56 µg/d infusion in cohort IIa or 112 µg/d infusion in cohort IIIa and 2 hours and 6 hours after the start of infusion of blinatumomab), day 19 (1 hour after pembrolizumab infusion has ended), day 26 (any time), and day 40 (any time) in cycle 1.

In the expansion cohort, blinatumomab PK samples will be collected on day 2 (any time), day 10 (any time), day 22 (any time), and day 29 (any time) in cycle 1.

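### SAP 10.6.10 lets samples taken before steady state into blinatumomab Css, and its clearance formula does not say that infusion rate and Css refer to the same dose

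*SAP*

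**What the plan says.** Blinatumomab PK parameters are a secondary endpoint (Protocol 10.1.1.2; SAP 4.1.2). SAP 10.6.10 names two of them.

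- **Css, cycle 1:** "summarized as the observed concentrations collected during continuous IV infusion by dose levels". No time window is attached. Parameters "will be estimated for patients who have evaluable PK data", and the SAP does not define evaluable.
- **Clearance:** "Systemic clearance (CL) calculated as" R0/Css, where R0 "is the infusion rate" in µg/hr and Css "is the dose normalized average" value. The normalization dose is not given, nor is it said whether R0 is the actual rate or the rate at that dose.

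Protocol 7.3.14.1 sets the Part 1 sampling times. On day 1 they are "predose, 4, 6, 8 h after start of 9" µg/day. On day 8 there is one sample 6 to 10 h after the step to 28 µg/day. On day 15 in cohorts IIa and IIIa there is a sample before the step to 56 or 112 µg/day, then samples "2 hours and 6 hours after the start of infusion of blinatumomab". The other cycle 1 samples are on day 2 and day 10, then days 15, 22, 29 and 43 (Ia) or days 19, 26 and 40 (IIa/IIIa).

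The sparser expansion-cohort schedule (days 2, 10, 22 and 29) will not be used, because SAP section 11 records the decision not to open Part 2.

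**The concern.** A concentration measured a few hours after an infusion starts, or after the rate is raised, is still climbing. Averaging it into Css can only pull the mean below the true plateau, and CL, which divides by Css, moves up by the inverse. The share of early samples differs by dose level, so the bias does too. A comparison of Css or CL across 9, 28, 56 and 112 µg/day could then suggest dose-dependent kinetics produced partly by the sampling schedule.

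The clearance sentence adds a second problem. Dividing an actual infusion rate by a concentration already scaled for dose leaves a dose factor in the result.

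The SAP summarizes these parameters by dose, so both problems bear on the comparison a reader would make first.

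**Working it through.** The SAP gives a rule and a formula here rather than a figure, so there is nothing to reproduce.

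**Step 1. Scheduled on-infusion samples at each dose level (Protocol 7.3.14.1)**

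| Dose level | Samples, time since start or step | Early (2 to 10 h) |
|---|---|---|
| 9 µg/day, all cohorts | 4, 6, 8 h; day 2 | 3 of 4 |
| 28, cohort Ia | 6–10 h; days 10, 15, 22, 29, 43 | 1 of 6 |
| 28, IIa/IIIa | 6–10 h; day 10; day 15 before the step | 1 of 3 |
| 56 (IIa) or 112 (IIIa) | 2, 6 h; days 19, 26, 40 | 2 of 5 |

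A subject in IIa or IIIa has 3 + 1 + 2 = 6 early samples out of 4 + 3 + 5 = 12.

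**Step 2. Size of the Css bias**

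Assume one-compartment accumulation. At time t after a start or step, the fraction of the new Css reached is

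f(t) = 1 − (1 − c0) × 2^(−t/h),

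where h is the half-life and c0 is the previous dose over the new dose: 0 for the first start, 9/28 for the step to 28, 28/56 = 0.5 for 56, and 28/112 = 0.25 for 112. Day 8 is taken at 8 h and day 2 at 24 h. The half-life is an assumption, because the documents do not give one.

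Worked cases:

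- 56 µg/day, h = 1 h: f = 0.875, 0.992, 1, 1, 1. Mean 0.973, so Css is about 3% low.
- 112 µg/day, h = 6 h: f = 0.405, 0.625, 1, 1, 1. Mean 4.030/5 = 0.806, so Css is 19% low and CL is 1/0.806 = 1.24 times true.
- 9 µg/day, h = 6 h: f = 0.370, 0.500, 0.603, 0.938. Mean 2.411/4 = 0.603, so Css is 40% low and CL is 1/0.603 = 1.66 times true.
- 28 µg/day in Ia, h = 6 h: f = 0.731, 0.997, then four values of 1. Mean 5.728/6 = 0.955, so Css is 4.5% low.

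Mean of scheduled samples over true Css:

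| Dose level | h = 1 h | 2 h | 4 h | 6 h |
|---|---|---|---|---|
| 9 | 0.98 | 0.89 | 0.72 | 0.60 |
| 28, Ia | 1.00 | 0.99 | 0.97 | 0.95 |
| 28, IIa/IIIa | 1.00 | 0.99 | 0.94 | 0.91 |
| 56 | 0.97 | 0.94 | 0.89 | 0.87 |
| 112 | 0.96 | 0.91 | 0.84 | 0.81 |

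With h = 4 h and a truly constant clearance, CL would appear as 1/0.72 = 1.39 times true at 9 µg/day, 1/0.97 = 1.03 at 28 in Ia, and 1/0.84 = 1.19 at 112.

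**Step 3. The clearance formula**

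Set true CL to 1. The actual rates are 9/24 = 0.375, 28/24 = 1.167, 56/24 = 2.333 and 112/24 = 4.667 µg/h, and true Css = R0/CL. Calculated CL over true CL:

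| Reading of the sentence | 9 | 28 | 56 | 112 |
|---|---|---|---|---|
| Actual R0 over un-normalized Css | 1 | 1 | 1 | 1 |
| R0 and Css both at one reference dose | 1 | 1 | 1 | 1 |
| Actual R0, Css scaled to 28 µg/day | 0.32 | 1 | 2 | 4 |
| Actual R0, Css per µg/day | 9 | 28 | 56 | 112 |

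The last row is also not in units of clearance. The sentence fits the last three rows, and only the first of those three is correct.

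**The case against.** The best defence of the Css rule is that the SAP calls the parameter a steady-state concentration and limits estimation to subjects with evaluable data, so a pharmacokineticist would leave out a sample drawn 2 h after a step. That may happen in practice. But the text that defines what is summarized sets no window, evaluable is undefined, and that limit selects subjects, not samples.

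It is also fair to say that the size is not known. It rests wholly on the assumed half-life, and at 1 h or less the bias is within about 4% at every dose level. In cohort Ia, where 28 µg/day is the target dose, it is small over the whole range assumed. This limits the size, not the direction.

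On clearance, normalizing is a coherent way to average across a subject's dose steps, and the sentence can be read correctly. That stands. A reader might infer from the literal wording that reported clearance will be wrong by factors of 9 to 112. The documents do not support this as a certain result: it needs one particular normalization combined with an un-rescaled rate.

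A reader might also infer that the geometric means will be undefined, because values below the quantification limit "were set to zero before data analysis". Geometric means are requested per parameter. A subject's averaged Css is zero only if every contributing sample is below the limit, and nothing in the documents indicates that this is expected. Dropping such values would bias the summary upward, so no change is proposed there.

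Finally, individual concentrations will be tabulated, so Css could be recomputed later. That reduces the harm but does not make the pre-specified summary right.

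**Conclusion.** The point holds in two parts.

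1. As written, the Css rule admits samples taken before steady state. The direction is certain given a rise towards a plateau: Css low and CL high, by amounts that differ across dose levels. The size is conditional. For an assumed half-life of 1 to 6 h under one-compartment accumulation, Css is about 3 to 19% low at 56 and 112 µg/day, 2 to 40% low at 9 µg/day, and 0 to about 5% low at 28 µg/day in cohort Ia.
2. The clearance formula is under-specified. It is correct if R0 and Css refer to the same dose; read literally, it makes CL scale with dose.

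This should be corrected, but it affects a descriptive secondary endpoint only. The DLT endpoint, the MTD definition and the stopping boundaries do not use Css or CL, and the DLRT's look at PK data is optional.

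**What to change.** Amend SAP 10.6.10 as follows.

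- Compute Css at each dose level only from samples taken after steady state at that level. Exclude the scheduled samples 2 to 10 h after a start or dose step, and keep them in the concentration-time tables. State what makes PK data evaluable.
- Define CL as the actual R0 over the un-normalized Css at that same dose. Alternatively, keep the normalization and name one reference dose for both terms.

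The cost is a few sentences and fewer samples behind each Css: 1 of 4 remains at 9 µg/day, 5 of 6 (Ia) or 2 of 3 (IIa/IIIa) at 28, and 3 of 5 at 56 or 112. At 9 µg/day the remaining day 2 sample, taken at 24 h, would have reached 1 − 2^(−24/6) = 0.94 of Css with a 6 h half-life, so that level should be reported with its single sample made plain. No new samples or visits are needed.

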10.6.11 Pharmacokinetic Analysis of Pembrolizumab

Pembrolizumab serum samples will be taken as listed in Schedule of Assessment of protocol. Pembrolizumab exposure parameters (eg, concentrations at the end of IV infusion and steady state trough concentrations) will be estimated for subjects who have evaluable PK data. Summary statistics, including mean, standard deviation, CV%, median, range (Minimal, Maximal), geometric mean and CV% of geometric mean will be

computed for each pharmacokinetic parameter by treatment cycles. Individual concentration-time data will be tabulated and presented in PK appendix. Mean concentration-time profiles may be provided, if sufficient data are available. **Analyses will be based on Pharmacokinetic Analysis Set**

10.6.12 Pharmacodynamic Analysis

Blood samples for biomarker analysis will be taken as described in the Schedule of Assessment of protocol. The cytokine levels over time will be analyzed with summary statistics by treatment period and treatment cohort. The changes in Lymphocytes (B-cell, T-cell populations, NK cells), leukocyte populations (leukocytes, lymphocytes, monocytes, and granulocytes) and Tumor PD-L1 expression over time will be summarized with descriptive statistics by treatment period and treatment cohort. Other analysis may be performed as appropriate. There will be a separate biomarker SSAP developed with a molecular scientist.

Merck biomarker lead will define analysis related to pembrolizumab and PD-L1.

Analyses will be based on Pharmacodynamic Analysis Set.

10.6.13 Exposure Response Analysis

PK data of blinatumomab may be subjected to exploratory population PK analysis with data from multiple studies. Nonlinear mixed effects modeling will be used for the analysis. Effect of covariates on exposure will be determined. These may include, age, body weight, body surface area, renal function, liver function, sex and selected baseline lab values. Other covariates may be analyzed as needed. Individual blinatumomab concentration data at time of interest may be used for the exposure response analysis.

Exposure-response relationships for selected efficacy and safety endpoints may be assessed as appropriate. The objectives and methodology of the exposure-response analysis will be provided in an E-R SSAP.

11. Changes From Protocol-specified Analyses

Because the decision was made not to proceed with Part 2 of the study. The primary analysis will now occur after the last subject in Part 1 has had an opportunity to complete response assessment during first 12 weeks since starting blinatumomab.

Other changes include modifications of the definitions to the following endpoints.

Secondary Endpoint (Per protocol):

Duration of response (DOR) for subjects with OR, (ie, CR and PR) by the Lugano Classification (Cheson et al, 2014) during the first 12 weeks since starting blinatumomab.

Changes from protocol:

Duration of response (DOR) for subjects with OR, (ie, CR and PR) by the Lugano Classification (Cheson et al, 2014) and Revised Response Criteria (Cheson et al, 2007) during the first 12 weeks since starting blinatumomab.

PFS definition (Per protocol):

The PFS will be calculated as the time from the date of first dose of blinatumomab until the date of diagnosis of progression of lymphoma, or date of death, whichever is earliest. For diagnosis of progression of lymphoma, the progression of radiographic assessment of PET-CT using Lugano Classification will be used. Subjects who are alive and did not have progression will be censored at the last radiological non-missing evaluable tumor assessment date. Progression free survival for subjects who were enrolled in dose cohorts that were not selected for the extension cohort will not be calculated.

Changes from protocol:

Progression Free Survival (PFS) by Lugano Classification:

The PFS will be calculated as the time from the date of first dose of blinatumomab until the date of diagnosis of progression of lymphoma, or date of death, whichever is earliest. For diagnosis of progression of lymphoma, the progression of radiographic assessment of PET-CT using Lugano Classification will be used. Subjects who are alive and did not have progression will be censored at the last radiological non-missing evaluable tumor assessment date.

Progression Free Survival (PFS) by Revised Response Criteria:

The PFS will be calculated as the time from the date of first dose of blinatumomab until the date of diagnosis of progression of lymphoma, or date of death, whichever is earliest. For diagnosis of progression of lymphoma, the progression of radiographic assessment of PET-CT using Revised Response Criteria will be used. Subjects who are alive and did not have progression will be censored at the last radiological non-missing evaluable tumor assessment date.

12. Literature Citations / References

Brookmeyer R and Crowley J. A confidence interval for the median survival time. *Biometrics*. 1982 ; 29-41.

Cheson, Bruce D., et al. "Revised response criteria for malignant lymphoma." *Journal of Clinical Oncology* 25.5 (2007): 579-586.

Cheson, Bruce D., et al. "Recommendations for initial evaluation, staging, and response assessment of Hodgkin and non-Hodgkin lymphoma: the Lugano classification." *Journal of clinical oncology* 32.27 (2014): 3059-3067.

Clopper CJ and Pearson EG. The use of confidence or fiducial limits illustrated in the case of the binomial. *Biometrika* 1934; 26(4): 404-413.

Gao, P, Ware, JH and Mehta, C Sample Size Re-estimation for Adaptive Sequential Design in Clinical Trials, *Journal of Biopharmaceutical Statistics*, 2008; 1184-1196

Kalbfleisch JD and Prentice RL. *The Statistical Analysis of Failure Time Data*. John Wiley, New York Rev, 1980; 4(2): 25.

13. Prioritization of Analyses

Not Applicable.

14. Data Not Covered by This Plan

Not Applicable.

15. Appendices

Appendix A. Technical Detail and Supplemental Information Regarding Statistical Procedures and Programs

Handling Incomplete Dates and Missing Dates for Adverse Events and Concomitant Medications.

The following data will be imputed using the following algorithm:

- Adverse Events
- Concomitant Medications

Imputation Rules for Partial or Missing Start Dates

Start Date		Stop Date						Missing
		Complete: yyyymmdd		Partial: yyyymm		Partial: yyyy		
		< 1 st dose	≥ 1 st dose	< 1 st dose yyyymm	≥ 1 st dose yyyymm	< 1 st dose yyyy	≥ 1 st dose yyyy	
Partial: yyyymm	= 1 st dose yyyymm	2	1	2	1	n/a	1	1
	≠ 1 st dose yyyymm		2		2	2	2	2
Partial: yyyy	= 1 st dose yyyy	3	1	3	1	n/a	1	1
	≠ 1 st dose yyyy		3		3	3	3	3
Missing		4	1	4	1	4	1	1

1 = Impute the date of first dose
 2 = Impute the first of the month
 3 = Impute January 1 of the year
 4 = Impute January 1 of the stop year

Note: If the start date imputation leads to a start date that is after the stop date, then do not impute the start date.

Imputation rules for partial or missing stop dates:

Initial imputation

- For partial stop date mmyyyy, impute the last of the month.
- For partial stop date yyyy, impute December 31 of the year.
- For completely missing stop date, do not impute.

- If the stop date imputation leads to a stop date that is after the death date, then impute the stop date as the death date.
- If the stop date imputation leads to a stop date that is before the start date, then there is a data error and do not impute the stop date. (ie. set the stop date as missing).

Imputation rules for partial or missing death dates:

- If death year and month are available but day is missing:
- If mmyyyy for last contact date = mmyyyy for death date, set death date to the day after the last contact date.
- If mmyyyy for last contact date < mmyyyy for death date, set death date to the first day of the death month.
- If mmyyyy for last contact date > mmyyyy for death date, data error and do not impute.

If both month and day are missing for death date or a death date is totally missing, do not impute.

Appendix B. Reference Values/Toxicity Grades

Laboratory Values

Safety laboratory values below a distinct limit (eg, detection limit, documented as “< [limit]”) will be substituted by half of the limit and values above a distinct limit (documented as “> [limit]”) will be substituted by the limit itself for all analyses. A Grade (based on CTC AE version 4.0 [v4.03: June 14, 2010]) will be assigned to each laboratory result as detailed in Table 6. Depending on the toxicity definition, the same result may be assigned to two grading for deviations towards higher or lower values. In case no lower limit of normal is provided for the absolute lymphocyte, neutrophils or leukocyte counts it will not be differentiated between grade 1 and grade 0 results for these parameters. Values not meeting any of the criteria will be assigned a grade 0.

Grading of Select Laboratory Parameters

Laboratory Parameter [Unit]	Grade 1	Grade 2	Grade 3	Grade 4
Lymphocytes [G/L]	0.8 - < LLN	0.5 - < 0.8	0.2 - < 0.5	< 0.2
Neutrophils [G/L]	1.5 - < LLN	1.0 - < 1.5	0.5 - < 1.0	< 0.5
Leukocytes [G/L]	3.0 - < LLN	2.0 - < 3.0	1.0 - < 2.0	< 1.0
Platelets [G/L]	75 - < LLN	50 - < 75	25 - < 50	< 25
Hemoglobin [g/L]*	100 - < LLN	80 - < 100	65 - < 80	< 65
Albumin [g/L]	30 - < LLN	20 - < 30	< 20	not defined
AST*	> ULN – 3*ULN	> 3*ULN – 5*ULN	> 5*ULN – 20*ULN	> 20*ULN
ALT *	> ULN – 3*ULN	> 3*ULN – 5*ULN	> 5*ULN – 20*ULN	> 20*ULN
GGT	> ULN – 2.5*ULN	>2.5*ULN – 5*ULN	> 5*ULN – 20*ULN	> 20*ULN
Bilirubin	> ULN – 1.5*ULN	>1.5*ULN – 3*ULN	> 3*ULN – 10*ULN	> 10*ULN
Fibrinogen^	%change of BL <25% or 0.75*LLN - < LLN	25%- <50% of BL or < 75*LLN – 0.5*LLN	50% - <75% of BL or < 0.5* LLN – 0.25*LLN	>= 75% of BL or < 50mg/dL or < 0.25*LLN

Laboratory Parameter [Unit]	Grade 1	Grade 2	Grade 3	Grade 4
Calcium [mmol/L]*	2.0 - < LLN	1.75 - < 2.0	1.5 - < 1.75	< 1.5
Potassium [mmol/L]*	not defined	3.0 - < LLN	2.5 - < 3.0	< 2.5
Lipase	> ULN – 1.5*ULN	> 1.5*ULN – 2.0*ULN	> 2.0*ULN – 5.0*ULN	> 5.0*ULN
Amylase	> ULN – 1.5*ULN	> 1.5*ULN – 2.0*ULN	> 2.0*ULN – 5.0*ULN	> 5.0*ULN

Page 2 of 2

BL baseline value, LLN: Lower limit of normal, ULN: Upper limit of normal

* Clinical criteria from CTC AE 4.0 grading were not considered in order to assign grades

^ In case of conflicting criteria the higher grade will be assigned, % change only used when baseline is <LLN

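### SAP Appendix B prints the fibrinogen grade 2 cut-off as 75 times LLN where 0.75 is evidently meant, and its percent-of-baseline criteria give no direction

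*SAP*

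**What the plan says.** The fibrinogen row of the grading table in SAP Appendix B reads as follows.

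- Grade 1: percent "change of BL <25% or 0.75*LLN - < LLN"
- Grade 2: "25%- <50% of BL or < 75*LLN – 0.5*LLN"
- Grade 3: "50% - <75% of BL or < 0.5* LLN – 0.25*LLN"
- Grade 4: ">= 75% of BL or < 50mg/dL or < 0.25*LLN"

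The row's footnote adds: "In case of conflicting criteria the higher grade will be assigned, % change only used when baseline is <LLN". The text above the table says: "Values not meeting any of the criteria will be assigned a grade 0".

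Fibrinogen is the last entry ("16. Fibrinogen") in the list in SAP Section 10.6.3. That list is introduced for summaries of actual values and changes from baseline. The same section then plans a graded output: "Shift tables between the worst post-baseline and baseline grades for selected laboratory parameters will be provided". It does not say which parameters those are.

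**The concern.** There are two separate faults in one row. The first is a numerical cut-off that does not fit its neighbours and, taken literally, puts the whole normal range into grade 2. The second is that the percent criteria never say decrease, although they are reserved for subjects who start below LLN, who are the ones with room to recover. Under the higher-grade rule a percent criterion met by a rise outranks the LLN band that the result falls in.

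What is at stake is the programmed laboratory grade and any shift table built on it. If normal results and mild falls all carry grade 2, the table cannot show a fall from normal into the grade 1–2 range. If rises count, a subject whose low fibrinogen recovers could be tabulated as having moved to grade 4.

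**Working it through.** **Inputs.** All cut-offs, the higher-grade rule, the limit on percent change and the grade 0 rule come from SAP Appendix B. The documents give no fibrinogen LLN. I assumed 150 and 200 mg/dL; the grades in the tables below are the same for both.

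**Step 1: do the LLN bands join up?** The upper edge of each grade should equal the lower edge of the next milder one.

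| Grade | Band as printed (× LLN) | Upper edge | Lower edge of milder grade |
|---|---|---|---|
| 4 | below 0.25 | 0.25 | 0.25, agrees |
| 3 | 0.25 to <0.5 | 0.5 | 0.5, agrees |
| 2 | 0.5 to <75 | 75 | 0.75, differs |
| 1 | 0.75 to <1 | 1 | – |

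75 / 0.75 = 100. Only the grade 2 upper edge fails. With LLN 200 mg/dL (2.0 g/L) it is 75 × 2.0 = 150 g/L, against 0.75 × 2.0 = 1.5 g/L for the evident intent. The lower edge is 0.5 × 2.0 = 1.0 g/L.

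**Step 2: grades for a subject with normal baseline (1.5 × LLN).** Percent change does not apply here.

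| Result (× LLN) | Grade as printed | Grade with 0.75 |
|---|---|---|
| 0.60, 0.74 | 2 | 2 |
| 0.80, 0.95 | 2 | 1 |
| 1.0, 1.5, 2, 3 | 2 | 0 |

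Grade 0 is lost because normal results now meet a criterion. Grade 1 is lost because the higher grade prevails when both bands are met. Values below 0.5 × LLN grade 3 or 4 in any case, so no realistic value ends at 0 or 1. In a shift table, a fall from 1.5 to 0.6 × LLN would read 2 to 2 instead of 0 to 2. A fall from 1.5 to 0.8 × LLN would read 2 to 2 instead of 0 to 1.

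**Step 3: grades for a subject with baseline below LLN.** Percent change = (result − baseline) / baseline. In the columns where rises count, signed and absolute change give the same grades for these cases.

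| Baseline to result (× LLN) | Change | As printed, rises count | Only 0.75 corrected | Only direction corrected | Both corrected |
|---|---|---|---|---|---|
| 0.5 to 0.75 | +50% | 3 | 3 | 2 | 1 |
| 0.5 to 0.9 | +80% | 4 | 4 | 2 | 1 |
| 0.5 to 1.0 | +100% | 4 | 4 | 2 | 0 |
| 0.8 to 1.4 | +75% | 4 | 4 | 2 | 0 |

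In units, with LLN 2.0 g/L: a baseline of 1.5 g/L rising to 2.7 g/L is (2.7 − 1.5) / 1.5 = 80%. That is grade 4 if rises count, grade 2 if only the direction is fixed (2.7 lies between 1.0 and 150 g/L), and grade 0 only if both faults are fixed.

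**Step 4: who is exposed to grade 4 on recovery?** A subject who just reaches LLN has risen by at least 75% when 1.75 × baseline ≤ LLN, that is, when baseline ≤ LLN / 1.75 = 0.571 × LLN. Because the shift table keeps the worst post-baseline grade, one such value is enough.

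**Step 5: a further reading.** The word change appears in the grade 1 cell and the footnote but not in the cells for grades 2 to 4. If those are read as a ratio to baseline, a stable low-baseline subject (100% of baseline) would also grade 4. The footnote makes the change reading more likely, but the cells do not settle it.

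**The case against.** The best reply is that the row corrects itself. The neighbouring cells show 0.75, Appendix B names CTCAE v4.03 as its basis, and SAP Section 9.7 requires outputs to be verified. A rule that grades nearly every normal result as 2 would be conspicuous. A decimal lost in converting the file also cannot be fully excluded, although every other decimal in the row survived. This makes harm from the first fault less likely. It does not make the printed cut-off right, and Appendix B is the text that programmers are told to follow.

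On direction, every absolute criterion in the row is on the low side, so a decrease is the natural meaning. That stands. A reader might infer that the percent criteria are a proven error, but the documents support only that the direction is unstated and that a wrong grade is therefore permitted. The limit to baselines below LLN does not settle it.

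On impact, three stronger inferences are tempting and not supported:

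- **That fibrinogen will certainly be in the shift tables.** Section 10.6.3 ties its list to the summaries of values and changes. Magnesium, direct bilirubin, alkaline phosphatase, LDH and immunoglobulins are on that list but have no grades in Appendix B, so the two sets cannot be equated. Fibrinogen is in both places, which makes its inclusion plausible but not stated.
- **That recovery would be reported as grade 4 toxicity of the combination.** A shift table shows laboratory grades without attribution. Investigators grade adverse events themselves under CTCAE (protocol Section 9.2.2.1).
- **That the primary endpoint is touched.** DLTs follow protocol Appendix E, with relatedness judged by the investigator.

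A real fall or recovery would also remain visible in the planned summaries of actual values and changes from baseline.

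**Conclusion.** The point holds, within limits. The grade 2 upper cut-off is wrong by a factor of 100 whatever the LLN. Followed literally, it removes grades 0 and 1 for fibrinogen. The missing direction is an ambiguity that allows a rise of 75% or more from a low baseline to be graded 4. The two faults are independent: correcting 75 to 0.75 alone leaves recovering subjects at grade 4, and correcting direction alone leaves normal results at grade 2.

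The consequence rests on two conditions: that the row is programmed as printed, with rises counted for the second fault, and that fibrinogen is among the unnamed shift-table parameters. If both hold, the tables would hide falls from normal into the grade 1–2 range and could show recovery as grade 4. Nothing beyond the programmed fibrinogen grades and outputs built on them is affected. The correction is still worth making, because this is an operational threshold in the grading specification and correcting it needs no new data or analysis.

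**What to change.** In the fibrinogen row of SAP Appendix B:

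- Change the LLN part of the grade 2 cell to <0.75 × LLN down to 0.5 × LLN.
- Write all four percent criteria as percent decrease from baseline: under 25% for grade 1, 25% to under 50% for grade 2, 50% to under 75% for grade 3, and 75% or more for grade 4. Apply them only to values below baseline, and only when baseline is below LLN.

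Both changes are needed. It would also help to name the shift-table parameters in Section 10.6.3, so that the use of the fibrinogen grade is explicit. The cost is a table correction in the SAP and a check that the grading program matches it. No data collection, endpoint or clinical rule changes.
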